2. INTRODUCTION

This statistical analysis plan (SAP) provides the detailed methodology for summary and statistical analyses of the data collected in Study C3791001.

2.1. Modifications to the Analysis Plan Described in the Protocol

Not applicable (NA).

2.2. Study Objectives, Endpoints, and Estimands

Type	Objective	Endpoint	Estimand
	Primary:	Primary:	Primary:

 Safety 	
 To characterize the safety and tolerability of isavuconazole through observation of TEAE. 	
Primary safety endpoint
 
 Incidence rates of TEAEs by SOC and PT. 	
 The incidence rates of TEAE by SOC and PT will be summarized without regard to adherence to the isavuconazole treatment and use of prohibited medication.
	Secondary:	Secondary:	Secondary:

 Efficacy 	
 To describe the efficacy of isavuconazole in the treatment of Chinese patients with IFD caused by Aspergillus species, and other filamentous fungi. 	
Key secondary efficacy endpoint:
 
 The percentage of all-cause mortality on Day 42 following primary treatment with isavuconazole. 
Other secondary efficacy endpoints:
 
 The percentage of all-cause mortality at Day 84 following primary treatment with isavuconazole. 	
 The percentage of all-cause mortality on Day 42 will be estimated in participants with IFD caused by Aspergillus species and other filamentous fungi, or IM, without regard to adherence to the isavuconazole treatment. The same estimand as above will be used to estimate the percentage of all-cause mortality at Day 84 in participants with IFD caused by

Type	Objective	Endpoint	Estimand
		
 The crude rate of overall response at EOT, Day 42, and 84; and the crude success rates of the clinical, mycological, radiological responses based on the investigators' assessment at EOT, Day 42, and 84. 	
Aspergillus species and other filamentous fungi.
 
 The crude rate of overall response, clinical response, mycological response and radiological response at EOT, Day 42, and Day 84 will be estimated in participants with IFD caused by Aspergillus species and other filamentous fungi, or IM while participants are on the isavuconazole treatment. Data collected after use of the prohibited medications will not be used. Participants who are not available for clinical, mycological or radiological responses will be considered as a failure for overall response.

 Safety 	
 To observe the additional safety and tolerability profile of isavuconazole. 	
Other secondary safety endpoints:
 
 Other AE summaries, including TEAE related to study intervention, Treatment-Emergent SAEs, TEAE leading to discontinuation of study intervention, TEAE leading to deaths, and all Deaths. Other safety variables, including clinical laboratory variables, vital signs, 12-lead ECG and eye examination. 	
 Not applicable Not applicable

 Pharmacokinetics 	
 To evaluate the PK of isavuconazole in the Chinese population with IFD caused by Aspergillus species and other filamentous fungi. 	
 Isavuconazole plasma concentrations at Day 3, 7, 14 and EOT visit. 	
 Not applicable
	Exploratory	Exploratory	Exploratory

 Efficacy 	
 To describe the efficacy of isavuconazole in the treatment of Chinese participants with IM. 	
 The percentage of all-cause mortality on Day 42 and 84 following 	
 The percentage of all-cause mortality on Day 42 and 84 will be estimated in participants with

Type	Objective	Endpoint	Estimand
		
primary treatment with isavuconazole.
 
 The crude rate of overall response at EOT, Day 42, and 84; and the crude success rates of the clinical, mycological, radiological responses based on the investigators' assessment at EOT, Day 42, and 84. 	
IM without regard to adherence to the isavuconazole treatment.
 
 The crude rate of overall response, clinical response, mycological response and radiological response at EOT, Day 42, and Day 84 will be estimated in participants with IM while participants are on the isavuconazole treatment. Data collected after use of the prohibited medications will not be used. Participants who are not available for clinical, mycological or radiological responses will be considered as a failure for overall response.

CCI

2.2.1. Primary Estimand(s)

The primary estimand of this study will use the treatment policy strategy and estimate the number and percentage of Treatment Emergent Adverse Events (TEAEs) by System Organ Class (SOC) and PT, without regard to adherence to the isavuconazole treatment and use of prohibited medication. The estimand is defined according to the primary objective and is in alignment with the primary endpoint. It includes the following 4 attributes:

- Population:** Participants who have proven, probable, or possible (invasive fungal disease) IFD caused by *Aspergillus* species, *Mucorales* species or other filamentous fungi as defined by the inclusion and exclusion criteria;
- Variable:** Number and percentage of TEAEs by SOC and PT;
- Intercurrent event(s):** Adherence to the isavuconazole treatment or the use of prohibited medication is not considered in the analysis. All data collected (after prohibited medication or after discontinuation of treatment) are included.

- Population-level summary: Number and percentage of participants with TEAEs divided by the number of participants in the population of interest.

2.2.2. Secondary Estimand(s)

Secondary estimands to assess secondary objectives will be:

Estimand 2.1: The key secondary estimand of this study will use the treatment policy strategy and estimate the percentage of all-cause mortality on Day 42 in participants with IFD caused by *Aspergillus* species and other filamentous fungi, or Invasive mucormycosis (IM), without regard to adherence to the isavuconazole treatment. The estimand is defined according to the secondary objective and is in alignment with the key secondary endpoint. It includes the following 4 attributes:

- Population: Participants who have proven, probable, or possible IFD caused by *Aspergillus* species, *Mucorales* species or other filamentous fungi as defined by the inclusion and exclusion criteria;
- Variable: Percentage of all-cause mortality on Day 42;
- Intercurrent event(s): Adherence to the isavuconazole treatment is not considered in the analysis. All data collected (after prohibited medication or after discontinuation of treatment) are included.
- Population-level summary: Number of participants with defined all-cause mortality divided by the number of participants in the population of interest.

Estimand 2.2: This estimand will use the treatment policy strategy and estimate the percentage of all-cause mortality at Day 84 in participants with IFD caused by *Aspergillus* species and other filamentous fungi, without regard to adherence to the isavuconazole treatment. It includes the following 4 attributes:

- Population: Participants who have proven, probable, or possible IFD caused by *Aspergillus* species, *Mucorales* species or other filamentous fungi as defined by the inclusion and exclusion criteria;
- Variable: Percentage of all-cause mortality at Day 84 ;
- Intercurrent event(s): Adherence to the isavuconazole treatment is not considered in the analysis. All data collected (after prohibited medication or after discontinuation of treatment) are included.
- Population-level summary: Number of participants with defined all-cause mortality divided by the number of participants in the population of interest.

Estimand 2.3: This estimand will use the while on-treatment policy strategy and estimate the crude rate of overall response, clinical response, mycological response and radiological

response at end of treatment (EOT), Day 42, and Day 84 in participants with IFD caused by *Aspergillus* species and other filamentous fungi, or IM while participants are on the isavuconazole treatment. Participants who are not available for clinical, mycological or radiological responses will be considered as a failure for overall response. It includes the following 4 attributes:

- **Population:** Participants who have proven, probable, or possible IFD caused by *Aspergillus* species, *Mucorales* species or other filamentous fungi as defined by the inclusion and exclusion criteria;
- **Variable:** Crude rate of overall response, clinical response, mycological response and radiological response at EOT, Day 42, and Day 84;
- **Intercurrent event(s):** All data collected after use of the prohibited medications will be excluded.
- **Population-level summary:** Number of participants with a success outcome divided by the number of participants in the population of interest.

2.2.3. Additional Estimand(s)

Estimand 3.1: This exploratory estimand will use the treatment policy strategy and estimate the percentage of all-cause mortality on Days 42 and 84 in participants with IM, without regard to adherence to the isavuconazole treatment. It includes the following 4 attributes:

- **Population:** Participants who have proven, probable, or possible IFD caused by *Mucorales* species as defined by the inclusion and exclusion criteria;
- **Variable:** Percentage of all-cause mortality on Days 42 and 84;
- **Intercurrent event(s):** Adherence to the isavuconazole treatment is not considered in the analysis. All data collected (after prohibited medication or after discontinuation of treatment) are included.
- **Population-level summary:** Number of participants with defined all-cause mortality divided by the number of participants in the population of interest.

Estimand 3.2: This exploratory estimand will use the while on-treatment policy strategy and estimate the crude rate of overall response, clinical response, mycological response and radiological response at EOT, Day 42, and Day 84 in participants with IM while participants are on the isavuconazole treatment. Participants who are not available for clinical, mycological or radiological responses will be considered as a failure for overall response. It includes the following 4 attributes:

- **Population:** Participants who have proven, probable, or possible IFD caused by *Mucorales* species as defined by the inclusion and exclusion criteria;

- **Variable:** Crude rate of overall response, clinical response, mycological response and radiological response at EOT, Day 42, and Day 84;
- **Intercurrent event(s):** All data collected after use of the prohibited medications will be excluded.
- **Population-level summary:** Number of participants with a success outcome divided by the number of participants in the population of interest.

2.3. Study Design

This is a single arm, prospective, multi-center study in Chinese patients with proven, probable, or possible IFD caused by *Aspergillus* species or other filamentous fungi.

Initially approximately 56 participants were planned to be enrolled in China and approximately 53 participants were expected to be treated. In protocol amendment 2, the sample size is modified to approximately 70 participants, among which approximately 66 participants are expected to be treated. The enrollment will be competitive.

Note: “Enrolled” means a participant’s, or their legally authorized representative’s, agreement to participate in a clinical study following completion of the informed consent process and assignment to study intervention. A participant will be considered enrolled if the informed consent is not withdrawn prior to participating in any study activity. Potential participants who are screened for the purpose of determining eligibility for the study, but do not participate in the study, are not considered enrolled.

All the participants will receive isavuconazole treatment. All participants receiving study medication will have the visits performed as scheduled. The longest treatment duration in this study is 84 days (maximum 180 days for participants with IM), and the total study duration for 1 participant is around 4 months (~7 months for participants with IM). For all participants, the Follow-up visit will take place 4 weeks (± 7 days) after the last administration of the study medication, and may occur before or after Day 42 and /or Day 84 (or Day 180 for participants with IM). Participants who need further antifungal treatment at the time of protocol defined longest treatment duration of isavuconazole may be switched to appropriate treatment at treating physician’s discretion.

The study will consist of 3 periods: Screening Period (up to 7 days), Treatment Period (maximum 84 days for participants with invasive aspergillosis (IA) or other filamentous fungi infection, or up to 180 days for participants with IM) and Follow-up Period (4 weeks after last dose of study intervention). Following the last dose of study intervention, participants who discontinued from the study intervention and participants who completed the treatment period will enter into a 4-week follow-up period for safety monitoring.

Participants fulfilling the criteria for “possible” IFD will be eligible for enrollment; efforts of further IFD categorization as “probable” or “proven” by culture and histology/cytology antigen (for *Aspergillus* and *Mucorales* species, including galactomannan (GM)) must be completed during the screening period. However, assessments performed up to 7 days after

the first administration of study intervention may be used to confirm the categorization of IFD.

3. ENDPOINTS AND BASELINE VARIABLES: DEFINITIONS AND CONVENTIONS

3.1. Primary Endpoint(s)

The primary endpoint is the incidence rates of TEAEs by SOC and PT. A TEAE is defined as any adverse event (AE) that starts on or after the first administration of study intervention until 28 days after last dose of study intervention.

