Radiology assessment (CT/HRCT/MRI)	X ^s		X ^o			X ^l	X ^l	X	X	X	
Bronchoscopic assessment ^l	X ^l		X ^o			X ^l	X ^l	X ^l	X ^l	X ^l	
Mycological assessment (Microbiology/Histopathology/Cytopathology/Tissue Nucleic Acid)	X			X ^l				X	X	X	
Neutropenic status/ANC	X		X Ongoing-----								→
Survival status ^k			X Ongoing-----								→

- Day related to start of study treatment (Day 1), Day -1 can be the same calendar day as Day 1.
- Anti-infective history taken within 4 weeks prior to the first dose of study intervention will be collected in the eCRF.
- All medication (except for anti-infective agents, T-cell & B-cell immunosuppressants and corticosteroids) given within 2 weeks prior to the first dose of study intervention will be collected in eCRF. T-cell & B-cell immunosuppressants given within 3 months prior to the first dose of study intervention, anti-infective agents and corticosteroids given within 4 weeks prior to the first dose of study intervention will be collected in eCRF.
- A serum β-hCG testing should be performed at screening for all WOCBP according to [Section 8.3.6](#). A negative serum or urine β-hCG test must be obtained before the first dose of study intervention.
- Samples/assessments obtained within 72 hours prior to the first dose of study intervention could be accepted as the Day 1 results.
- Study intervention administration will occur every day from Day 1 to Day 84 (Day 180 for IM) or EOT.
- Adverse events will be recorded from the sign-off of informed consent to at least 28 days after last dose of study intervention.
- Only in participants with abnormalities observed at EOT.
- On Day 1, vital signs will be measured within 1 hour before and 1 hour after the end of each study intervention administration.

Period	Screening	Study Treatment									Follow-Up
Visit Identifier	Screening D-7 to D-1	Day 1	Day 2 ^p	Day 3 ^p	Day 7 ^p	Day 14 ^p	Day 28 ^p	Day 42 ^k	Day 84 ^{k,q} /Every 42 days after Day 84 ^q	End of Treatment (EOT) ^{k,m} or Discontinuation	Post Treatment Follow-up ^k (4 weeks after EOT)
Visit Window (Day) ^a					±2	±3	±3	±7	±7	±3	±7

- j. Measuring once prior to study intervention administration.

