8.4.1. Time Period and Frequency for Collecting AE and SAE Information

The time period for actively eliciting and collecting AEs and SAEs (“active collection period”) for each participant begins from the time the participant provides informed consent, which is obtained before undergoing any study-related procedure and/or receiving study intervention, through and including a minimum of 28 calendar days, except as indicated below, after the last administration of the study intervention.

Follow-up by the investigator continues throughout the active collection period and until the AE or SAE or its sequelae resolve or stabilize at a level acceptable to the investigator.

When a clinically important AE remains ongoing at the end of the active collection period, follow-up by the investigator continues until the AE or SAE or its sequelae resolve or stabilize at a level acceptable to the investigator and Pfizer concurs with that assessment.

For participants who are screen failures, the active collection period ends when screen failure status is determined.

If the participant withdraws from the study and also withdraws consent for the collection of future information, the active collection period ends when consent is withdrawn.

If a participant permanently discontinues or temporarily discontinues study intervention because of an AE or SAE, the AE or SAE must be recorded on the CRF and the SAE reported using the CT SAE Report Form.

Investigators are not obligated to actively seek information on AEs or SAEs after the participant has concluded study participation. However, if the investigator learns of any SAE, including a death, at any time after a participant has completed the study, and they consider

the event to be reasonably related to the study intervention, the investigator must promptly report the SAE to Pfizer using the CT SAE Report Form.

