9.3.2. Safety Analyses

Safety variables will be summarized descriptively for the safety population. 95% CIs for the binary outcome of selected safety variables may be presented based on an exact binomial distribution.

The primary safety endpoint is the incidence rates of TEAEs by SOC and PT. A TEAE is defined as any AE that starts on or after the first administration of study intervention until 28 days after last dose of study intervention. Other key summaries of AEs include the summaries of

- TEAE related to study intervention
- Treatment-Emergent SAEs
- TEAE leading to discontinuation of study intervention
- TEAE leading to deaths
- All deaths

Vital signs will be listed and summarized by means and standard deviation (SD). Laboratory test values will be presented in change from baseline and shift tables and by individual listings with flagging of values outside the normal reference ranges. ECG findings will be presented by listings and frequency tables, as appropriate.

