10.3.1. Definition of AE

AE Definition

• An AE is any untoward medical occurrence in a participant or clinical study participant, temporally associated with the use of study intervention, whether or not considered related to the study intervention.• Note: An AE can therefore be any unfavorable and unintended sign (including an abnormal laboratory finding), symptom, or disease (new or exacerbated) temporally associated with the use of study intervention.

Events Meeting the AE Definition

• Any abnormal laboratory test results (hematology, clinical chemistry, or urinalysis) or other safety assessments (eg, ECG, radiological scans, vital sign measurements), including those that worsen from baseline, considered clinically significant in the medical and scientific judgment of the investigator. Any abnormal laboratory test results that meet any of the conditions below must be recorded as an AE:
• Is associated with accompanying symptoms.• Requires additional diagnostic testing or medical/surgical intervention.• Leads to a change in study dosing (outside of any protocol-specified dose adjustments) or discontinuation from the study, significant additional concomitant drug treatment, or other therapy.• Exacerbation of a chronic or intermittent preexisting condition, including an increase in either frequency and/or intensity of the condition.• New condition detected or diagnosed after study intervention administration, even though it may have been present before the start of the study.• Signs, symptoms, or the clinical sequelae of a suspected drug-drug interaction.• Signs, symptoms, or the clinical sequelae of a suspected overdose of either study intervention or a concomitant medication. Overdose per se will not be reported as an AE or SAE unless it is an intentional overdose taken with possible suicidal/selfharming intent. Such overdoses should be reported regardless of sequelae.

Events **NOT** Meeting the AE Definition

- Any clinically significant abnormal laboratory findings or other abnormal safety assessments that are associated with the underlying disease, unless judged by the investigator to be more severe than expected for the participant's condition.
- The disease/disorder being studied or expected progression, signs, or symptoms of the disease/disorder being studied, unless more severe than expected for the participant's condition.

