- For each AE or SAE, the investigator **must** document in the medical notes that they have reviewed the AE or SAE and have provided an assessment of causality.

- There may be situations in which an SAE has occurred and the investigator has minimal information to include in the initial report to the sponsor. However, **it is very important that the investigator always make an assessment of causality for every event before the initial transmission of the SAE data to the sponsor.**
- The investigator may change their opinion of causality in light of follow up information and send an SAE follow up report with the updated causality assessment.
- The causality assessment is one of the criteria used when determining regulatory reporting requirements.
- If the investigator does not know whether or not the study intervention caused the event, then the event will be handled as “related to study intervention” for reporting purposes, as defined by the sponsor. In addition, if the investigator determines that an SAE is associated with study procedures, the investigator must record this causal relationship in the source documents and CRF, and report such an assessment in the dedicated section of the CT SAE Report Form and in accordance with the SAE reporting requirements.

Follow-Up of AEs and SAEs

- The investigator is obligated to perform or arrange for the conduct of supplemental measurements and/or evaluations, as medically indicated or as requested by the sponsor, to elucidate the nature and/or causality of the AE or SAE as fully as possible. This may include additional laboratory tests or investigations, histopathological examinations, or consultation with other healthcare providers.
- New or updated information will be recorded in the originally submitted documents.
- The investigator will submit any updated SAE data to the sponsor within 24 hours of receipt of the information.

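### The TEAE definition uses the AE start date alone, so whether a screening AE that worsens on isavuconazole enters the primary endpoint depends on how the site records it

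*SAP*

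**What the plan says.** The same rule appears in three places. SAP 3.1 defines a TEAE as "any adverse event (AE) that starts on or after the first administration of study intervention until 28 days after last dose of study intervention". Protocol 9.3.2 states: "A TEAE is defined as any AE that starts on or after the first administration of study intervention until 28 days after last dose". The protocol synopsis repeats it under statistical methods. SAP 3.5.1, 6.1 and 6.6.1 add no rule for an AE that began before dosing and then worsened.

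Collection starts earlier than the TEAE window. Protocol 8.4.1 says that the active collection period "begins from the time the participant provides informed consent", and a footnote to the schedule of activities agrees: "Adverse events will be recorded from the sign-off of informed consent to at least 28 days after last dose of study intervention". Screening can last up to 7 days (SAP 2.3).

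Two further passages bear on worsening:

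- Protocol 10.3.1 lists among events that meet the AE definition: "Exacerbation of a chronic or intermittent preexisting condition, including an increase in either frequency and/or intensity of the condition". It also includes clinically significant laboratory or other safety results that worsen from baseline.
- Protocol 10.3.3, on follow-up of AEs, says: "New or updated information will be recorded in the originally submitted documents".

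**The concern.** AEs with a pre-dose onset should be expected, because these are acutely ill patients observed from consent. If such an AE worsens after the first dose and the site updates the existing record, the start date stays before dosing and the event fails the TEAE test. It is then missing from the primary endpoint and from every table built on TEAEs in SAP 6.6.1: by severity, treatment-related, serious and leading to discontinuation.

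An on-treatment deterioration is what a safety endpoint is meant to show. TEAE incidence is the primary endpoint, and the sample size rests only on the chance of seeing at least one participant with a 3% AE. Transaminase elevation, which the synopsis names as a potential risk, is the kind of finding that may already be on record before dosing. Sites that record the same course differently would also produce different primary-endpoint data.

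**Working it through.** **1. One clinical course recorded in two ways.** This example is hypothetical. A mild ALT increase is entered as an AE on Day -3. It becomes severe on Day 10 and isavuconazole is stopped.

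| Recording | Basis in the protocol | Start date | TEAE under SAP 3.1? |
|---|---|---|---|
| Original record updated | 10.3.3, follow-up of AEs | Day -3 | No |
| New AE opened at the worsening | 10.3.1, worsening meets the AE definition | Day 10 | Yes: severe, and leading to discontinuation |

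Section 10.3.1 says what qualifies as an AE. It does not say that an AE already on the CRF receives a new record and onset date when it worsens. Section 10.3.3 says where updates go, but does not address a change of severity. Neither passage settles the case.

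**2. Direction.** The first recording can only remove a participant from a numerator. The denominator, the safety population, does not change. Any error is therefore downward.

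**3. Where it would show.** SAP 6.1 counts a participant once per term. A PT count loses a participant only if that participant has no other on-treatment record of the same PT, and a SOC count only if there is no other TEAE in that SOC. The rate of any TEAE would hardly move if it is as high as the 96% that protocol 2.2.4 reports for isavuconazole in the pivotal aspergillosis study. The exposure is in individual PTs and in the severity, related, serious and discontinuation tables.

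**4. The plan's own figure.** Inputs from protocol 9.5 are n = 66 treated and an AE rate of 3%.

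- 1 − (1 − 0.03)^66 = 0.8661, against a stated 86.6%.
- For the former n = 53, 1 − 0.97^53 = 0.8010, against a stated 80%.

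Both reproduce.

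**5. Illustration of size.** Let f be the share of participants with a given 3% treatment-emergent AE who have it only as an uncounted worsening of a screening AE. The documents give no value for f, so the values below are assumptions. The probability of at least one counted participant is 1 − (1 − 0.03(1 − f))^66.

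| Assumed f | Counted rate | Probability | Change from 86.6% |
|---|---|---|---|
| 5% | 2.85% | 85.2% | −1.4 points |
| 10% | 2.70% | 83.6% | −3.0 points |
| 20% | 2.40% | 79.9% | −6.7 points |

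**The case against.** A reader might infer that a screening AE that worsens can never be a TEAE. The documents do not support that. Protocol 10.3.1 makes worsening an AE in its own right. Both 10.3.1 and SAP 3.5.1 make an abnormality an AE if it leads to a change in dosing or to discontinuation. In the example, the Day 10 result qualifies independently and, if entered as such, is counted.

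Four further arguments can be made for the plan:

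- **The exposed group is narrow.** An abnormality already present at consent is medical history or a baseline finding, and its later worsening would be a new AE with an on-treatment start. Only an AE that is first recorded between consent and first dose is at risk. That interval is at most about 7 days and can be under one, since the schedule lets Day -1 fall on the same date as Day 1.
- **The follow-up sentence in 10.3.3 is general.** It follows text on supplementary investigations and does not mention onset dates.
- **The convention may be set elsewhere.** Protocol 10.1.7 refers to CRF completion requirements, which are not among the documents available.
- **Other outputs catch part of the worsening.** SAP 6.6.2 tabulates ALT and AST thresholds and creatinine increases on all post-baseline values, 6.6.4 tabulates QTcF changes, and 6.6.1 lists SAEs and deaths.

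The first point stands and limits the size. The second and third mean that the loss is possible rather than certain. They leave the protocol and SAP silent on a matter that decides whether a primary-endpoint event is counted. The fourth is a partial safeguard outside the primary endpoint. The laboratory shift table treats low-to-low and high-to-high as no change, so a value that worsens within its abnormal category shows no shift there. AEs without a laboratory or ECG measurement have no comparable table.

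**Conclusion.** The concern holds in a limited form. The definition has no worsening clause. For an AE first recorded between consent and first dose, inclusion in the primary endpoint depends on a recording convention that neither document states. Any resulting error lowers reported incidence. It is worth correcting because it affects the primary endpoint and the correction is small.

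The number of participants affected is probably small and cannot be derived from the documents. The detection probabilities of 85.2% to 79.9% rest wholly on assumed values of f from 5% to 20%.

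A reader might also conclude that the stated 86.6% is wrong. It is not: it is the correct binomial probability for 66 participants and a 3% rate, and a worsening clause would change neither the sample size nor that figure. A guess at the total number of worsening screening AEs across all terms should not be set against 3% of 66 either, because that benchmark applies to a single AE.

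**What to change.** In SAP 3.1, protocol 9.3.2 and the synopsis, define a TEAE as an AE that starts on or after the first dose, or that started before it and increases in severity or becomes serious on or after it, in both cases up to 28 days after the last dose. A pre-dose AE that leads to discontinuation without having worsened need not be added.

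Make sure that the CRF and its completion requirements capture the date of worsening, through either a new record dated at the change or a dated severity change on the existing record. All sites should use the same method.

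Cost: a clause in each of three places and a CRF completion note. Reported incidences may rise slightly. Protocol section 9 requires major modifications of the primary endpoint definition to be reflected in a protocol amendment, so the sponsor must decide whether this qualifies. If it does, the approvals in protocol 10.1.1 apply: the ethics committee and, for a substantial amendment, the health authority.
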